8.3 Exploratory Endpoint	18
8.4 Handling of Missing Values	19
8.5 Multiplicity Adjustments.....	19
8.6 Subgroup and Site Effects	19
9 Statistical Methodology for Safety Endpoints	19
9.1 Safety Parameters.....	19
9.1.1 Analysis and Presentation of Safety Parameters	19
9.1.2 Adverse Events	19
9.1.3 Physical Examination.....	20
9.1.4 Vital Signs	20
9.1.5 Electrocardiogram (ECG)	20
9.1.6 Laboratory Safety Data.....	20
9.1.7 CT Scans.....	22
9.2 Safety Update.....	22
10 Deviations from Protocol	22
11 Software	22
12 Reference List.....	23
13 List of Listings	24

14 List of Tables 25
15 List of Figures 31

Change Log

Version number	Date	Change
1.0	28NOV2019	Original version
2.0	27JAN2020	
Analysis set for listings updated to all subjects in section 5.1 and section 12.
 
SAS program inserted as part of section 7.2.5.
 
List of output for safety update has been updated in section 8.2.
 
QTcF has been added to the list of endpoints in section 8.1.5.

3.0	21JAN2021	
Description of early termination added in section 3.2.
 
Section 5.2 about issues caused by the COVID-19 pandemic has been added including 5 new outputs.
 
Listing of screen failures and the definition of a subject being terminated early have been added to section 5.3.
 
A table of last visit attended before closure is added in section 6.1. Furthermore, relative exposure has been defined and two outputs have been added to the same section.
 
A table and a listing of non-serious adverse events have been added in section 7.1. Furthermore, tables of adverse events and non-serious adverse events by preferred term with frequency $\geq 5\%$ have been added to this section.
 
Responder endpoints and their analyses have been deleted from section 7.2.3
 
Summary of evaluation of vital signs has been removed from section 8.1.4
 
Summary of evaluation of ECG has been removed from section 8.1.5

1 List of Abbreviations

ADR	Adverse Drug Reaction
ALT	Alanine Aminotransferase
AST	Aspartate Aminotransferase
AE	Adverse Event
aPAP	autoimmune Pulmonary Alveolar Proteinosis
ATC	Anatomical Therapeutic Chemical Classification System
BMI	Body Mass Index
CI	Confidence Interval
CRF	Case Report Form
CT	Computed Tomography
DBL	Data Base Lock
DSS	Disease Severity Score
ECG	Electrocardiogram
FAS	Full Analysis Set
GGT	Gamma Glutamyl Transpeptidase
HEENT	head, eyes, ears, nose, and throat
LLOQ	Lower Level of Quantification
MCH	Mean cell haemoglobin
MCV	Mean cell volume
MedDRA	Medical Dictionary for Regulatory Activities
N	Number of Subjects
PT	Preferred Term
SAE	Serious Adverse Event
SAP	Statistical Analysis Plan
SD	Standard Deviation
6MWD	6-minute walk distance
6MWT	6-minute walk test
SGRQ	St Georges Respiratory Questionnaire
SOC	System Organ Class
TEAE	Treatment Emergent Adverse Event
WLL	Whole Lung Lavage

2 Introduction

The statistical analysis plan (SAP) for the trial SAV006-03 is based on the final protocol version 5.0 24AUG2018.

The SAP describes in detail the analyses to be conducted and highlights any deviations from the analysis described in the protocol (see section 9). Deviations from methods described in this SAP, if any, will be specified in the clinical trial report.

The analysis is performed based on:

- The clinical database, which includes the electronic Case Report Forms (eCRF)

Reporting of the trial will be after the date of last subject last visit except for a safety update during the trial.

The trial is terminated early, and the final reporting will be done when all subjects have attended a final visit and the database is considered clean and locked.

3 Trial Characteristics

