10.8.4. Electrocardiogram (ECG)

A 12-lead ECG will be assessed using a standard ECG machine according to local procedures at the time points shown in [Table 1](#). No central overreading will be performed.

Heart rate, QRS, PR and QT intervals will be recorded from the ECGs. The ECGs will be interpreted and signed and dated by the investigator or his/her designee. Results will be classified as normal, having a non-clinically significant abnormality, or having a clinically significant abnormality. All clinically significant abnormalities will be recorded as AEs.

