11. STATISTICS

No formal sample size calculation was done as this is an open-label extension trial. Up to 90 subjects will be included.

Data will be summarised using summary statistics. Continuous data will be presented with the number of observations, mean value, standard deviation, minimum, quartile 1, median, quartile 3 and maximum value. Categorical data will be presented as counts and percentages. The data will be presented by visit in tables and graphs. Individual subject data will be listed. Further details of all analyses will be given in the statistical analysis plan.

No “analysis sets” (intention to treat, per protocol, etc.) are defined. All subjects will be included in the analyses/data presentations (equivalent to a Full Analysis Set).

Only recorded data will be analysed/presented and any subjects who have missing data will only have observed data reported, with no imputation for missing data.

Interim cuts of data may be done on a yearly basis and as needed for regulatory purposes (e.g. 120-day safety update).

Data listings will show all recorded data.

Data from the trial is planned to be combined with relevant data from the IMPALA trial; these combined analyses will be reported separately.

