8.1.4 Vital Signs

Vital signs (heart rate, temperature, systolic and diastolic blood pressure) will be measured at each visit including an evaluation for each parameter.

Continuous values of vital signs will be summarized by parameter and visit including change from baseline.

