8.1.5 Electrocardiogram (ECG)

A 12-lead ECG will be assessed using a standard ECG machine according to local procedures at the time points shown in Table 1.

Heart rate, QRS, PR and QT intervals will be recorded from the ECGs. The ECGs will be interpreted and signed and dated by the investigator or his/her designee.

The QT interval by be corrected using Fridericia's formula (QTcF) will be added to the summary tables as described below.

Continuous values of ECG will be summarized by parameter and visit including change from baseline.

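### SAP version 3.0 drops the count of the investigator's ECG and vital-sign evaluations, so abnormalities not reported as treatment-emergent AEs, category shifts and large QTcF changes are counted in no table, and SAP section 9 does not say so

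*SAP*

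**What the plan says.** **Collection.** Protocol 10.8.4 has each ECG read locally, without central over-reading, and put into one of three categories: "Results will be classified as normal, having a non-clinically significant abnormality, or having a clinically significant abnormality". Protocol 10.8.3 has vital signs assessed as normal or abnormal, and abnormal findings graded as clinically significant or not. The flow chart schedules both at Visits 1 to 7; Visit 1 may use the final IMPALA visit. SAP 8.1.4 still describes the collection: vital signs "will be measured at each visit including an evaluation for each parameter".

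**Presentation promised.** Protocol section 11: "Categorical data will be presented as counts and percentages", with data presented by visit. The same section leaves further detail to the SAP.

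**Presentation planned.** SAP 8.1.4: "Continuous values of vital signs will be summarized by parameter and visit including change from baseline". SAP 8.1.5: "Continuous values of ECG will be summarized by parameter and visit including change from baseline", with QTcF added. The list of tables has 14.3.2.1 and 14.3.2.2 for vital signs and 14.3.3.1 and 14.3.3.2 for ECG. None shows the evaluation.

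**How it came about.** The change log for version 3.0, dated 21 January 2021, records "Summary of evaluation of vital signs has been removed from section 8.1.4" and "Summary of evaluation of ECG has been removed from section 8.1.5". It gives no reason. SAP section 2 says deviations from the protocol's analysis are highlighted in section 9. Section 9 lists two: the added safety analysis set and the unreported time-off-treatment endpoint.

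**The concern.** Long-term safety is the primary objective, and the trial is uncontrolled and descriptive. A harm confined to a few subjects is therefore best seen by counting those subjects. The investigator's evaluation is collected at every clinic visit and is naturally shown as a count. Without it, a reader of the tables cannot tell how many subjects moved from normal to abnormal unless the finding became an AE.

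QTcF raises the same question in another form. Sites record QT; the SAP adds the Fridericia correction to its summary tables. No table counts subjects above a QTcF limit, and a site that judged an uncorrected QT cannot be assumed to have reported a QTcF outlier as an AE.

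The departure also goes unexplained in the section that the SAP reserves for departures.

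**Working it through.** The plan has no figure to reproduce on this point. Protocol section 11 states: "No formal sample size calculation was done as this is an open-label extension trial". The check compares what is collected with what is tabulated, followed by one illustration.

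**1. Outputs that could carry the information**

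| Output | Source | What it shows | What it leaves out |
|---|---|---|---|
| Four tables of continuous values | SAP 5.1, Tables 14.3.2.1 to 14.3.3.2 | N, mean, SD, median, minimum, maximum; change from baseline | Evaluation category; number of subjects beyond a limit |
| Two listings | 16.2.9.1, 16.2.9.2 | Individual data for all subjects | Any count; the reader must tally |
| 23 AE tables | SAP 7.1 and 8.1.2, Tables 14.3.1.1 to 14.3.1.23 | Events, subjects and proportions for findings reported as treatment-emergent AEs | Abnormalities that did not become AEs; events outside the window |
| Tables of the evaluation | none | – | – |

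**2. How far the AE tables reach**

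- Protocol 10.8.4 requires clinically significant ECG abnormalities to be recorded as AEs.
- Protocol 10.9.2.5 makes an asymptomatic abnormal vital sign an AE if it is clinically significant, meets an SAE criterion or causes the subject to discontinue the trial.
- SAP 8.1.2 admits to the safety summaries only events with onset from first exposure in this trial to seven days after the estimated last drug date.
- Protocol 10.9.2 groups related signs under one diagnosis where possible. Protocol 10.9.2.5 treats an abnormal vital sign that accompanies a symptom as additional information. Such findings may not be recognisable as ECG or vital-sign findings in the AE tables.

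Three things are therefore counted nowhere: abnormalities not reported as treatment-emergent AEs, shifts in category from baseline, and subjects with large QTcF values or changes.

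**3. Illustration for QTcF**

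Inputs:

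- Subjects: SAP 3.2 gives 60 enrolled and 55 on active treatment at termination. The safety set is everyone exposed in the trial, so it lies between 55 and 60.
- Assumed, not in the documents: three subjects rise by 60 ms at a visit, the others have no mean change, and the background SD of change is 15, 20 or 25 ms.

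Mean change = 3 × 60 / 55 = 3.3 ms (3 × 60 / 60 = 3.0 ms with 60 subjects).

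Standard error with 55 subjects, including the variance that the three outliers add:

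- Added variance = 60² × 3 × 52 / (55 × 54) = 189.1 ms²
- SE = √((SD² + 189.1) / 55)
- SD 15: √(414.1 / 55) = 2.7 ms
- SD 20: √(589.1 / 55) = 3.3 ms
- SD 25: √(814.1 / 55) = 3.8 ms

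The mean shift is 0.9 to 1.2 standard errors, so the mean does not reveal the pattern.

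The maximum does better. For normally distributed changes with SD 20, its expected value is that of the largest of 55 draws: about 46 ms with no outliers and about 77 ms when three of the 55 are shifted by 60 ms. It signals that someone is extreme, but not whether it is one subject or three. A count above a change limit answers that.

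**The case against.** The strongest reply is that the design sends these findings to AE reporting on purpose. Protocol 4.2 says safety is assessed through AEs and that clinically significant ECG changes will be reported as such. The primary endpoint is AE counts, and the ECG and vital-sign evaluations are not endpoints. The sentence on categorical data in protocol section 11 is a general format rule, the details are left to the SAP, and no protocol section promises an evaluation table. Local readings without central over-reading also make a noisy variable. All of this stands, and it keeps the point modest. It does not supply the missing counts, and a line in section 9 would still have been in order.

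Four stronger readings are tempting, and the documents do not support them.

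- *That ECG and vital signs are reported only as visit means.* SAP 5.1 also gives SD, median, minimum and maximum. Change-from-baseline tables and listings are planned as well, and protocol section 11 says listings will show all recorded data.
- *That no abnormal result is counted.* Clinically significant findings reported as treatment-emergent AEs are counted by events, subjects and proportions.
- *That restoring the evaluation table would reveal the three subjects in the illustration.* The category covers the whole ECG, and nothing ties it to QTcF. A subject already rated abnormal but not significant at baseline could stay there. Only a QTcF limit count would show them.
- *That the removal was selective reporting.* Version 3.0 is dated after the stated end of treatment (end of 2020) in an open-label trial. But the change log states both removals openly, the same version adds AE outputs, and nothing shows that results drove the change.

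**Conclusion.** The point holds as a limited reporting gap. The evaluation is collected at each clinic visit and tabulated nowhere. Abnormalities outside the treatment-emergent AE route appear only in listings, shifts from baseline are not counted, and neither are large QTcF values or changes. SAP section 9 is silent, although SAP section 2 says deviations are highlighted there.

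It is worth correcting because safety is the primary objective and the remedy is cheap. No planned figure is wrong, and clinically significant treatment-emergent findings are not lost.

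The size given is illustrative. A mean shift of 3.0 to 3.3 ms rests on an assumed three subjects with a 60 ms rise and on a safety set of 55 to 60; the standard errors of 2.7 to 3.8 ms also rest on an assumed SD of 15 to 25 ms. The SAP does not say whether the ECG and vital-sign listings will show the evaluation category; protocol section 11 implies that they will.

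**What to change.** In SAP 8.1.4 and 8.1.5, on the safety analysis set and by the existing three columns plus total:

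- Add, for ECG and for each vital sign, either a count-and-percentage table of the evaluation by visit or a shift table from the baseline evaluation (as defined in SAP 5.1) to the worst evaluation after first dose in this trial. Use the categories in protocol 10.8.3 and 10.8.4.
- Add the number and percentage of subjects above absolute and change limits for QTcF. Fix the limits before database lock.
- Add a footnote that evaluations are local, without central over-reading of ECGs, and may vary between investigators.

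If the evaluation tables stay out, state the departure and its reason in SAP section 9.

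The cost is two or three tables from data already in the eCRF, and no new data. The drawback is the variation between local readers, which the footnote covers.

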3.1 Trial Objectives

3.1.1 Primary Objective

The primary objective is to investigate safety of long-term use of inhaled molgramostim.

3.1.2 Secondary Objectives

The secondary objectives are

- To investigate effects of long-term use of inhaled molgramostim on oxygenation.
- To investigate effects of long-term use of inhaled molgramostim on exercise capacity.
- To investigate effects of long-term use of inhaled molgramostim on respiratory quality of life.
- To investigate requirement for WLL during long term use of inhaled molgramostim.
- To investigate effects of long-term use of inhaled molgramostim on lung function.
- To investigate maintenance of effect after discontinuation of inhaled molgramostim.

3.2 Trial Design

The trial is an open-label, non-controlled, multi centre clinical trial of inhaled molgramostim in autoimmune pulmonary alveolar proteinosis (aPAP) patients.

Subjects with aPAP who have completed the IMPALA (MOL-PAP-002) trial will be eligible for this trial.

At the baseline visit, eligible subjects may continue or re-start treatment with inhaled molgramostim (300 µg) administered intermittently in cycles of seven days molgramostim, administered once daily, and seven days off treatment.

Trial visits will be conducted at 6-monthly intervals until the end of trial. Participating subjects will be encouraged to contact the clinic between visits if they experience adverse events (AEs) or worsening of aPAP, or if they have any other concerns.

During the trial, Whole Lung Lavage (WLL) will be applied as rescue therapy. The criterion for performing WLL is clinical worsening of aPAP based on symptoms, reduced exercise capacity and/or findings of hypoxemia or desaturation according to the investigator's judgement. The reason(s) for conducting WLL will be documented. Subjects undergoing WLL will continue treatment with molgramostim, unless discontinuation is medically required, according to investigator's discretion.

Subjects may discontinue molgramostim due to remission of aPAP, lack of response that requires a different treatment modality, or AEs. Subjects becoming pregnant will be required to discontinue treatment with molgramostim. Subjects who discontinue molgramostim will be encouraged to continue in the trial and attend visits according to the same schedule until end of the trial. Molgramostim treatment may be re-started if medically required. Subjects not requiring treatment at the Baseline visit may start molgramostim treatment during the trial if medically required.

Savara received advice on the MOL-PAP-002 trial results from EMA and FDA. The data demonstrated more favorable evidence of efficacy on the continuous dosing regimen. Following the advice Savara has subsequently decided to conduct an additional Phase III confirmatory trial to support future registration of the continuous dosing regimen. The SAV006-03 trial investigates an intermittent dosing regimen but considering the MOL-PAP-002 clinical trial results and the received health authority advice there will not be adequate efficacy and safety data on the intermittent dosing regimen to support a marketing authorization application for this regimen. Consequently, Savara has decided to discontinue the SAV006-03 trial and support the continued clinical investigation of the continuous dosing regimen in a new trial.

60 subjects have been enrolled in the SAV006-03 trial and enrolled subjects will be able to continue treatment until end of 2020. Of these, 55 subjects are on active treatment and 5 subjects do not receive treatment at the time of trial termination. The 5 subjects have been allowed to remain in the trial to observe development of their disease without receiving treatment.

The data from the SAV006-03 trial will be included in the ongoing safety evaluation of molgramostim nebulizer solution. The results of the SAV006-03 trial will also be included as part of a potential future marketing authorization application for use of molgramostim nebulizer solution as a potential treatment for autoimmune pulmonary alveolar proteinosis, although the intermittent dosing regimen will likely not be included as a treatment regimen under posology.

All generated data will be cleaned and assessed according to plan and will contribute to the risk-benefit profile for molgramostim. The trial will be reported according to ICH GCP requirements.

Table 1 Activities flow chart

Table 1: Visit	Visit 1	Visit 2	Visit 3	Visit 4	Visit 5	Visit 6	Visit 7	FU TC	Unscheduled
	Baseline ^a	Month 6	Month 12	Month 18	Month 24	Month 30	Month 36	2 wks after trial completion	
Time	0	Week 26	Week 52	Week 78	Week 104	Week 130	Week 156		
Visit Window	N/A	± 4wks	± 4 wks	± 4 wks	± 4 wks	± 4 wks	± 4 wks	+ 1 wk	
Informed consent	X								
Eligibility criteria	X								
Demographics	X								
Concomitant medication	X	X	X	X	X	X	X		X
WLL information ^b	X	X	X	X	X	X	X		X
Pregnancy test and contraceptive check ^c	X	X	X	X	X	X	X		(X) ^d
Physical Exam	(X)		X		X		X		(X) ^d
Vital signs	(X)	X	X	X	X	X	X		(X) ^d
ECG	(X)	X	X	X	X	X	X		(X) ^d
Blood gas analysis ^e	(X)†	X	X	X	X	X	X		(X) ^d
Lung function tests ^f	(X)†	X	X	X	X	X	X		(X) ^d
6MWT ^g	(X)†	X	X	X	X	X	X		(X) ^d
Quality of Life (SGRQ)	(X)†	X	X	X	X	X	X		
DSS	(X)†	X	X	X	X	X	X		(X) ^d
Overall Clinical Assessment	X	X	X	X	X	X	X		X
CT Scan	(X) ^d	(X) ^d	(X) ^d	(X) ^d	(X) ^d	(X) ^d	(X) ^d		(X) ^d

Table 1: Visit	Visit 1	Visit 2	Visit 3	Visit 4	Visit 5	Visit 6	Visit 7	FU TC 2 wks after trial completion	Unscheduled
	Baseline ^a	Month 6	Month 12	Month 18	Month 24	Month 30	Month 36		
Time	0	Week 26	Week 52	Week 78	Week 104	Week 130	Week 156		
Visit Window	N/A	± 4wks	± 4 wks	± 4 wks	± 4 wks	± 4 wks	± 4 wks	+ 1 wk	
Laboratory Safety Analyses ^h	(X)	X	X	X	X	X	X		(X) ^d
AEs	X	X	X	X	X	X	X	X	X
PK samples (Italy only) ⁱ	X	X	X	X	X	X			
Medical history	X								
Dispense trial drug ^j	X	X	X	X	X	X			(X) ^d
Subject Diary Card ^k	X	X	X	X	X	X	X		
Compliance		X	X	X	X	X	X		(X) ^d
Study continuation or termination ^l		X	X	X	X	X	X		(X) ^d

FU = follow-up, TC = telephone call, WLL = whole lung lavage

^a Baseline (Visit 1) may coincide with the final visit of the IMPALA (MOL PAP 002) trial; if so, assessments performed at Visit 11 (for subjects enrolled under protocol MOL PAP 002 version 4.0 or later), or Visit 13 (subjects enrolled under a protocol version prior to version 4.0) may serve as the baseline assessments for this protocol. If more than 3 months have elapsed since completion of the IMPALA study to Baseline (Visit 1) the assessments must be repeated.

^b Requirement for WLL and if required, indication for procedure will be recorded. If WLL is performed date of WLL and type of WLL (unilateral, bilateral) will be recorded.

^c Serum pregnancy test at Baseline (Visit 1) and at all subsequent visits during treatment with inhaled molgramostim (pregnancy tests for subjects not receiving trial drug are not mandatory). A urine pregnancy test will also be performed at dosing at Baseline (Visit 1) to immediately confirm that the subject is not pregnant and meets the inclusion criterion for treatment. If treatment is not dispensed at Baseline (Visit 1) the urine pregnancy test will instead be performed at the first visit treatment is dispensed. Subjects will be requested to do monthly urine testing at home during treatment.

^d Only applicable if assessment is done according to clinical practice or medical need, e.g. in case of a clinical deterioration. If done, results will be recorded

^e Capillary sampling for blood gas analysis may be used instead of an arterial blood gas sample at sites that routinely use this method.

^f DLCO, FEV₁, and FVC (absolute values and % of predicted values).

^g 6MWT includes assessment of SpO₂ and Borg CR10 score for dyspnoea before, during (SpO₂) and after (Borg) the test. If the subjects used supplemental O₂ during the procedure in IMPALA, the same O₂ flow will be used at the subsequent tests in this trial, if possible.

^h Haematology and clinical chemistry

ⁱ For Italy only: Patients will have their visits scheduled for an on-treatment week within the allowed window of +/- 4 weeks. The first sample must be taken just prior to inhalation of molgramostim. The 2nd sample must be taken 2 hours post dosing, (+/- 10 minutes).

- ^j Trial drug is dispensed to subjects who require treatment according to investigator's discretion. **For Italy only:**
The visit should take place in during the week on treatment. On the day of dosing, the subjects will do the nebulization at the clinic, in order to collect pre-dose PK sample.
- ^k Diary card to collect safety information to be given to the subject and collected at the next visit. The subject will be asked to record any AEs they have experienced, enter dates for pregnancy tests taken at home (if applicable) and dates for changing of the nebuliser mouthpiece in the subject diary.
- ^l If the planned trial termination has been declared since the subject's last visit in the trial, the subject will leave the trial.

